3.4. Determination of Sample Size

In order to evaluate the minimal effective daily dose of rhNGF eye drops, a Williams design has been chosen [1] [2]. For this study three treatment groups have been considered: rhNGF eye drops solution 20 µg/mL TID; rhNGF eye drops solution 20 µg/mL BID plus vehicle eye drop solution SID; vehicle eye drop solution TID.

To this purpose, the sample size has been determined applying the formula reported in the publication Chow et al., 2008 at page 301 [3]

The sample size calculation for the primary variable is based on the following assumptions:

- The probability level (α) for one-sided test is set at 0.025 (see table 12.1.2 at page 298 in Chow et al., 2008[3]) and the power level at approximately 90%.
- DELTA, in change from baseline between treatments, of 5.3 and Standard Deviation for DELTA of 10.78. Both DELTA parameters are derived from results of co-variance analysis obtained from study NGF0216 in the subset of hyposecretive patients (i.e., excluding "evaporative-only" patients).

According to this calculation, 87 patients per treatment group (for a total of 261 patients) are adequate to observe the planned difference assumed for the minimum effective daily dose. Assuming a drop-out of about 15%, a total of 300 is the target number of patients proposed to be enrolled.

The inclusion of at least 60 subjects with documented diagnosis of Primary Sjögren's Syndrome within the planned 300 patients will have no impact on the initial study assumptions (Standard Deviation of 10.78 and DELTA of 5.3 mm) because the patients could have been enrolled based on the previous criteria on which sample size was based. Moreover, a similar prevalence of patients with Primary Sjögren's Syndrome has already been reported in the NGF0216 medical history (~25% of patient the FAS population).

Impact on the power of the study due to stopping enrollment in the study to 261 randomized subjects:

This document is confidential.

With 261 patients randomized, assuming a drop out rate of 15%, only 228 patients in total (76 patients by group) are considered adequate to observe the planned difference assumed for the minimum effective daily dose.

With 76 patients by group, with a DELTA, in change from baseline between treatments of 5.3 and Standard Deviation for DELTA of 10.78, the power to detect a difference will be at least 85%.

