3.5. Treatment Assignment & Masking

Eligible patients will be randomized in a 1:1:1 ratio to either rhNGF eye drops solution 20 µg/mL TID (100 patients) or rhNGF eye drops solution 20 µg/mL BID plus vehicle eye drop solution SID (100 patients) or vehicle eye drop solution TID (100 patients).

Following amendment n° 1 to the protocol, randomization will be stratified according to absence/presence of a documented diagnosis of Primary Sjögren's Syndrome.

The study was ongoing at the time of amendment and at the beginning of September 135 patients had already been randomized. The randomization list generated on March 22, 2019 will be stopped when the last randomization number used will be at the end of a block. Moving forward, the replacement list will be used. According to the amendment n° 1, the replacement randomization schedule will be stratified according to absence/presence of a documented diagnosis of Primary Sjögren's Syndrome.

Each randomized patient after amendment will be allocated with randomization number, according to the stratified randomization list using an Interactive Web Response System (IWRS). Drop outs after randomization will not be replaced.

Randomization lists as well as associated kit numbers will be generated by a member of Syneos Health Biostatistics department, not involved in the conduct of the study.

Patients will be assigned to treatment in numerical order. A tear-off label from the kit box, with the kit number, will be attached to the investigational product dispensing log.

The enrollment of patients will be scheduled in order to assure an inclusion of approximately 240 patients without Primary Sjögren's Syndrome diagnosis and at least 60 patients with Primary Sjögren's Syndrome.

For patients already enrolled in the study, the assignment to a strata will be based on Medical history form (see section 8.1).

The identity of the treatments will remain unknown to the patient, Investigator, site staff and Sponsor's clinical research personnel until the study is unmasked for the final statistical analysis (after data base lock) except in case of specific events that will require unmasking of the patient.

The vials containing rhNGF (20 µg/mL) or vehicle will be identical in appearance, and the contents of the vials will be indistinguishable. All staff directly involved in the analysis of study results will remain masked to treatment assignments while the study is in progress.

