8.2. Secondary Efficacy Endpoints and Analyses

The same exploratory sensitivity analysis will be also conducted for SANDE, Schirmer Test II, Corneal and Conjunctiva Vital Staining and TFBUT.

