8.2.4. Change from Baseline in Tear film break-up time (TFBUT)

Descriptive statistics (actual and change from baseline) for TFBUT will be presented by treatment and visit. Comparison (descriptive in nature) of the change from baseline of each treatment versus placebo will be performed by means of a t-test at each timepoint.

Change from baseline in TFBUT at Week 4 will be analyzed in a similar manner as the Change from baseline to Week 4 in Schirmer test I.

TFBUT values will be listed.

8.2.5. Number of Patients who Experienced a Worsening in Symptom Scores (SANDE) and/or NEI Score $\geq 50\%$ Assessed at Week 4

Number and percentage of patients who experienced a worsening in symptom scores (SANDE) and/or NEI score $\geq 50\%$ assessed at Week 4 will be summarized by treatment group.

Difference, between treatment group (Each active dose – Placebo), in the percentage of patients who experienced a worsening will be tested using a chi-square test.

This document is confidential.

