3) Sample Code for Exploratory sensitivity Efficacy Analysis : Schirmer test I

```
PROC MIXED DATA=SCHIRMERI;
CLASS STRATA TRT01P ;
MODEL chg = TRT01P STRATA STRATA*TRT01P /solution;
lsmeans STRATA*TRT01P / pdiff cl at time=Week4;
```

4) Sample Code for Efficacy Analysis : IDEEL and EQ-5D-3L

```
PROC MIXED DATA=IDEEL;
CLASS usubjid TRT01P visit;
MODEL chg = TRT01P visit TRT01P * visit /ddfm=kr;
repeated visit / sub = usubjid type = un;
lsmeans TRT01P*visit / cl pdiff;
lsmeans TRT01P / cl pdiff;
```

5) Sample Code for Efficacy Analysis: PGIC

A Wilcoxon rank sum test will be used for PGIC. An example of the SAS code to perform this analysis is reported below.

```
*****
```

* SAS Code: Wilcoxon

* Variables in the model:

* aval = value of PGIC

*trt01pn = treatment planned

```
*****;
```

```
PROC NPAR1WAY DATA=PGIC WILCOXON;
WHERE TRT01P in ("Placebo" "Dose 1");
CLASS TRT01P;
VAR AVAL;
RUN;
```

6) Sample Code for Efficacy Analysis: Proportion of subjects with worsening in SANDE and/or NEI score>=50%

```
*****
```

This document is confidential.

* SAS Code: Wilcoxon

* Variables in the model:

* aval = worsening in symptom scores (SANDE) and/or NEI score $\geq 50\%$: yes or No

*trt01pn = treatment planned

*****;

```
PROC FREQ DATA=Prop;
  WHERE TRT01P in ( "Placebo" "Dose 1");
  TABLES trt01p*aval / chisq;
  RUN;
```

This document is confidential.

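### The overall comparisons for PGIC and for worsening leave out the Primary Sjögren factor used to stratify randomisation after amendment 1, and no confidence interval is specified for the worsening difference

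*SAP*

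**What the plan says.** **Randomisation.** SAP 3.5 says that, following amendment 1, "randomization will be stratified according to absence/presence of a documented diagnosis of Primary Sjögren's Syndrome". By early September 135 patients had already been randomised from the unstratified list. SAP 8.1 assigns patients enrolled before the amendment to a stratum from the medical history form.

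**PGIC.** SAP 8.2.7 plans a frequency table by treatment and visit, plus Wilcoxon p-values for each dose against placebo. Appendix I item 5 repeats this ("A Wilcoxon rank sum test will be used for PGIC"), and its code carries treatment only.

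**Worsening.** SAP 8.2.5 reports number and percentage per group. The difference between each active dose and placebo "in the percentage of patients who experienced a worsening will be tested using a chi-square test". The code in Appendix I item 6 is "TABLES trt01p*aval / chisq", with no stratum variable and no request for a risk difference or interval. Protocol 9.5 also specifies a chi-square test for this endpoint.

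**Where the factor is used.** SAP 8.1 plans an exploratory model with the Sjögren factor and its interaction with treatment for Schirmer I. SAP 8.2 extends it: "The same exploratory sensitivity analysis will be also conducted for SANDE, Schirmer Test II, Corneal and Conjunctiva Vital Staining and TFBUT". PGIC and worsening are not on that list. Under SAP 6.6 all secondary endpoints are summarised within each stratum. The table index has presence and absence tables for worsening (14.2.2.5.2, .3, .5, .6) and for PGIC (14.2.2.7.2, .3, .5, .6).

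**The concern.** When a trial stratifies its randomisation, the comparison of arms is normally made within strata and then combined. If the stratum predicts outcome, a pooled rank or chi-square test leaves the between-stratum spread in the noise and gives up power. A chance imbalance in Sjögren patients from the unstratified first list also stays in the overall comparison. For these two endpoints no planned analysis of the whole population addresses either matter.

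The missing interval is a separate gap and the more useful one to close. The worsening endpoint exists to show whether patients deteriorate on active treatment. With a p-value and two percentages, a reader can subtract, but is given no planned statement of how large an excess the data leave open.

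**Working it through.** **1. The plan's own figures.** The documents give no rate, effect or power for PGIC or worsening, so only the Schirmer I calculation can be reproduced. SAP 3.4 gives "DELTA, in change from baseline between treatments, of 5.3 and Standard Deviation for DELTA of 10.78", and an alpha that "for one-sided test is set at 0.025".
- n per group = 2 × (1.960 + 1.282)² × (10.78/5.3)² = 86.9, so 87 per group and 261 in total, as stated.
- Power at 76 per group: 5.3 / (10.78 × √(2/76)) = 3.03; 3.03 − 1.96 = 1.07; Φ(1.07) = 85.8%, against the stated value of at least 85%.

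These agree. They supply the range of 76 to 87 per arm used below and say nothing else about this point.

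**2. PGIC: plain Wilcoxon against van Elteren.** Everything here except the 76 per arm is an assumption: 23% Sjögren (between the planned 20% and the roughly 25% cited from NGF0216), seven ordered categories and their proportions, a latent treatment effect of 0.47 SD, two-sided 0.05. The simulation used 20,000 runs per case, with van Elteren weights 1/(n+1).

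| Sjögren patients worse by | Wilcoxon | van Elteren | Gain (points) |
|---|---|---|---|
| 0 SD | 78.8% | 78.3% | −0.5 |
| 0.5 SD | 76.9% | 78.0% | +1.1 |
| 0.75 SD | 75.0% | 78.1% | +3.1 |
| 1 SD | 72.1% | 77.9% | +5.8 |

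The size of both tests stays near 5%.

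**3. Worsening: chi-square against stratified CMH.** Assumptions: 76 per arm, 20% Sjögren, odds ratio of 1 to 4 between Sjögren status and worsening, two-sided 0.05; 40,000 runs per case.
- Size with 20% worsening in non-Sjögren patients in both arms: chi-square 4.0 to 5.0%, CMH 4.7 to 4.9%.
- Power at 30% against 15% (non-Sjögren rates): 61% and 61% at odds ratio 1; 63% and 63 to 64% at odds ratio 2; 61 to 62% and 64 to 65% at odds ratio 4 (chi-square first).

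The gain is about 0 to 3 points.

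**4. Precision of the worsening difference.** 95% half-width = 1.96 × √(2p(1−p)/n), with p assumed equal in both arms.
- p = 10%, n = 76: 1.96 × √(0.18/76) = 9.5 points.
- p = 10%, n = 87: 1.96 × √(0.18/87) = 8.9 points.
- n = 76, p = 5%, 20%, 30%: 6.9, 12.7 and 14.6 points.

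At n = 76 the chi-square test has 41.6% exact power for 10% against 20%. A doubling of worsening would therefore be non-significant more often than not.

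**5. Imbalance from the unstratified list.** 135/3 = 45 per arm. The SD of the between-arm difference in Sjögren count is √(2 × 45 × p(1−p)): 3.8 patients at p = 0.20 and 4.1 at p = 0.25. A difference of 4 patients in 76 with a 0.5 SD stratum effect moves the mean by 4/76 × 0.5 = 0.026 SD, against a standard error of √(2/76) = 0.16 SD. This is minor.

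**The case against.** A fair defence has several parts.

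- **The omission is plan-wide.** The primary analysis of variance has treatment only, and the IDEEL and EQ-5D mixed models have treatment, visit and their interaction. This stands: nothing is peculiar to these two endpoints, except that Schirmer I and the four endpoints named in SAP 8.2 at least have an exploratory stratum model.
- **The gain rests on assumptions.** No figure in the documents supports a stratum shift in PGIC or worsening. This stands, and so the gain is given as a range that includes a small loss.
- **The stratum is imperfect.** At most 261 − 135 = 126 patients were randomised within strata. For those enrolled before the amendment, a medical history entry of Sjögren without the word primary counts as absence (SAP 8.1). Misclassification would shrink the gain.
- **76 is not necessarily the analysis number.** SANDE and staining are carried forward at Week 4 in the FAS, so worsening can be derived for many dropouts. Hence the range up to 87.
- **The output is not fully visible.** Appendix I is sample code, and the table templates are in a separate document. An interval might appear there, but the SAP text does not call for one.
- **The chi-square is the protocol's own test.** This stands, and the fix keeps it.

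A reader might go further and infer that the factor is not used at all for these endpoints, that no effect size is reported for worsening, or that worsening is the only endpoint recording deterioration. The documents support none of these. Both endpoints are tabulated by stratum in the FAS and the PP set. Percentages are reported per group and their difference is named. PGIC runs to very much worse, and EQ-5D has shift tables from baseline.

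**Conclusion.** The point holds as a modest improvement and does not show an invalid analysis. Neither overall comparison uses the stratification factor, and no confidence interval is specified for the worsening difference. It would be tempting to read the unstratified tests as biased or as inflating type I error. The simulations do not show that: size stays at or a little below the nominal level.

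The cost is power: about 1 to 6 points for PGIC under assumed shifts of 0.5 to 1 SD, and about 0 to 3 points for worsening. If the stratum is not prognostic, stratifying PGIC loses under one point. The more practical gap is the interval, which at 10% worsening would be about ±9 to ±9.5 points. Nothing in the plan says that a non-significant chi-square will be read as absence of worsening, but the specified output gives no guard against that reading. These are secondary endpoints, and the primary conclusion is unaffected.

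**What to change.** Before database lock:

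1. **PGIC (SAP 8.2.7, Appendix I item 5).** Use the van Elteren test stratified by Primary Sjögren status for each dose against vehicle, for example PROC FREQ with TABLES strata*trt01p*aval / CMH2 SCORES=MODRIDIT.
2. **Worsening (SAP 8.2.5, Appendix I item 6).** Report the stratum-weighted risk difference, each dose minus vehicle, with its 95% CI in Tables 14.2.2.5.1 and 14.2.2.5.4. Keep the protocol's chi-square test and add a stratified CMH test in support. State that a non-significant p-value is not evidence of no excess worsening.
3. **SAP section 11.** Record both changes. Also list the existing move of PGIC to Wilcoxon: Protocol 9.5 has PGIC analysed like the primary endpoint, and section 11 does not mention the change.
4. **Appendix I item 6.** Correct the code header, which says Wilcoxon above a chi-square analysis.

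The cost is SAP wording and a few lines of code, with no new data. The downsides are under one point of power if the stratum is not prognostic, and possible misclassification of the stratum for patients enrolled before the amendment, which should be acknowledged beside the results.
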